1.3 Endpoints

- The primary endpoint will be the total number of AK/NMSC in the treatment areas compared to the control areas.
- Time to occurrence to first AK/NMSC compared to the control areas.
- Changes in karyometry from baseline in the treatment and non treatment fields.
- Changes on the sun damage scale compared to the control areas.
- Mean pain score between the treatment field locations.

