Togsverd-Bo et al [28] found that repeated PDT sessions in renal transplant patients could serve as primary prevention for skin dysplasia. In their randomized controlled trial, 15 patients with clinically normal skin received PDT red light at inclusion and at 6 month intervals. PDT significantly delayed the onset of AK compared to untreated areas. They observed AK in 63% of patients in untreated skin compared to 28% in PDT treated skin at 3 years.

These findings are further supported by molecular studies, which mirror the clinical response, showing that PDT can reverse or reduce field cancerization but that one single dose is not sufficient to achieve these results [29,30]. For example, Bagazgoitia and colleagues have shown that two or more treatments of PDT can

delay the appearance of AKs, reduce histological features of actinic damage, and decrease expression of early markers of carcinogenesis such as K1-67 and p53 [29]. Sun-damaged skin has a higher baseline expression level of p53 than non-sun-damaged skin, and p53 and p53 family members may be important mediators of cell death signaling in photodynamic therapy of cancer [32]. This again underscores the need for repeated PDT sessions with vigilant follow-up when using this field therapy for cancer prevention. In addition, karyometric analysis has been used successfully to detect nuclear changes from sun-damaged skin to actinic keratosis to squamous cell carcinoma, and to provide sensitive, quantitative method to assess the efficacy of prevention interventions [33-36].

Associated Risks

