10. PHARMACOKINETIC STUDIES

10.1 Collection

One skin biopsy with a 4-mm punch will be taken from each forearm (treatment and non treatment sites) prior to the first session and another skin biopsy with a 4-mm punch will be taken at the end of all the sessions at 3 years, on each forearm of all patients for a total of 4 biopsies per patient. Gelfoam or 1-2 sutures will be used to close the biopsy site.

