10.2 Processing

All skin biopsy specimens will be sent and processed at the University of Arizona Cancer Center in Tucson, in [name] laboratory..Karyometry analysis will be done at [name] laboratory for all specimens. Karyometric measures of nuclear abnormalities scores will be recorded for statistical analysis.

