16. STATISTICAL CONSIDERATIONS

Characteristics of study subjects will be summarized by appropriate abstract statistics, including frequency, proportion and 95% Clopper-Pearson confidence interval (CI) for the proportion for categorical variables, median, and range for continuous variables.

Evaluable subjects for safety outcome measures will be those who complete any study visits or those who discontinue the study treatments due to adverse events (AE).
Evaluable subjects for efficacy outcome measures will be those who complete all study visits. At least 15-16 evaluable subjects for each of these analyses are expected.

Primary efficacy outcome measure will be the difference in the total number of AK/NMSC in the treatment areas compared to the control areas. All unique AK/NMSC

observed during the 3 year study period will be identified and summed in each area. The statistical significance of the difference will be tested using the Wilcoxon Signed-Rank Test.

Secondary safety and efficacy measure: Time to the occurrence of the first AK/NMSC in the control versus treated areas will be estimated using the Kaplan-Meier estimate. Changes in the p53 staining from baseline to end of treatment will be evaluated using McNemar's Test. Mean pain scores (VAS) and photo damage scale global scores of the study population will be compared with each respectively using Wilcoxon Signed-Rank Test.

Sample Size Determination: Safety will be evaluated using a one-sided confidence interval (as the lower bound is not of interest). At least fourteen patients will be evaluable for safety. If none of the patients have an adverse primary safety outcome, the upper bound of a 95% one-sided confidence interval is < 20%.

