17.2 Efficacy Analysis

Number of AK/NMSC will be counted for each site using the photographs of the treatment and the control areas. AKs will be graded by thickness I-III: I = mild, slightly palpable, II = moderate, easily felt, III= severe, very thick. NMSC, including basal cell carcinoma, Bowen's disease and squamous cell carcinoma, will be diagnosis and confirmed histologically by biopsy.

Photo damage in the treatment and control fields will be assessed by the sun damage scale as: absent, mild, moderate, and severe. The scale includes 4 points: fine wrinkling, coarse wrinkling, abnormal pigmentation and global (0-10). Ratings for epidermal dysplasia will be obtained by immunohistochemistry of p53 staining of skin biopsies in the treatment areas at baseline and after the last treatment.

Time to occurrence of AK/NMSC will be calculated from the first visit to the development of an AK or NMSC in the treatment areas and in the control areas.

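### p53 is rated on the treated forearm only and tested before versus after, so a change cannot be attributed to PDT, while the listed two-forearm karyometry endpoint has no planned test

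*Combined protocol and SAP*

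**What the plan says.** **p53.** Section 17.2 obtains the rating by "p53 staining of skin biopsies in the treatment areas at baseline and after the last treatment". Section 16 then says "Changes in the p53 staining from baseline to end of treatment will be evaluated using" McNemar's test. It names no side and no contrast with the control side.

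Section 17.2 does name the control side for its other measures. Lesions are counted in both areas, time to occurrence is calculated for both, and "Photo damage in the treatment and control fields will be assessed by the sun damage scale".

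**Biopsies taken.** Section 10.1: "One skin biopsy with a 4-mm punch will be taken from each forearm (treatment and non treatment sites) prior to the first session", and again at 3 years "on each forearm of all patients for a total of 4 biopsies per patient". Section 7.1 randomizes which side is treated and leaves the other as the untreated control.

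**Karyometry.** Section 1.3 lists "Changes in karyometry from baseline in the treatment and non treatment fields" as an endpoint. Section 10.2 applies karyometry to every specimen and adds "Karyometric measures of nuclear abnormalities scores will be recorded for statistical analysis". Footnote F of the Section 26 schedule gives karyometry, from baseline to end of treatment, as the use of the biopsies. Sections 16 and 17 do not mention it.

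p53 shows the reverse pattern: it has a test in Section 16 but does not appear in Sections 1.3, 10.2 or 26. No score or cut-off is defined, although McNemar's test needs a two-category result.

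**The concern.** A 3-year change on one forearm mixes any effect of PDT with whatever moves both forearms: sun behaviour, immunosuppression, ageing of the skin, or differences between staining batches. The design provides a concurrent, randomized control forearm to remove these influences, and the p53 analysis does not use it.

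Two wrong conclusions are possible. First, Section 4.4 reports that repeated PDT can "decrease expression of early markers of carcinogenesis such as K1-67 and p53", so a significant fall on the treated side would readily be read as confirmation, though the test would give the same result if the control forearm had fallen equally. Second, this is a primary-prevention trial. PDT may work by holding treated skin steady while control skin worsens, and a treated-only test cannot see that benefit.

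Meanwhile the biopsy endpoint that does have a control side would be reported without a prespecified summary, contrast or test.

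**Working it through.** The plan gives no figure for p53 or karyometry to reproduce: no prevalence, cut-off, alpha or power. Its only sample-size figure concerns safety and has no bearing here.

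**Inputs from the documents.** Treated-side ratings at two times (17.2); McNemar's test (16); 15-16 evaluable subjects (16); both forearms biopsied at both times (10.1).

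**Assumptions not in the documents.** p53 is positive or negative; exact tests; two-sided alpha 0.05; the two forearms change independently. Drift means a change from baseline common to both forearms and unrelated to PDT. The documents give neither its size nor its direction.

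**Treated-only test.** On one forearm let *u* be the chance of turning positive and *d* the chance of turning negative. With *b* and *c* sites changing each way,

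P(b, c) = n! / [b! c! (n−b−c)!] × u^b × d^c × (1−u−d)^(n−b−c),

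and p = min{1, 2 × P(Bin(b+c, 0.5) ≤ min(b, c))}. If all changes go one way, 5 changes give 2 × 0.5^5 = 0.0625 and 6 give 2 × 0.5^6 = 0.031. At least 6 of the 15-16 sites must therefore change. The rejection rate is the sum of P(b, c) over outcomes with p < 0.05.

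**Between-side test.** Apply the same sign test to treated change minus control change in each patient. With T for treated, C for control and s = 1−u−d:

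- P(difference > 0) = u_T(1−u_C) + s_T d_C
- P(difference < 0) = d_T(1−d_C) + s_T u_C

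Example with no PDT effect, d = 0.50 and u = 0.05 on both sides: 0.05 × 0.95 + 0.45 × 0.50 = 0.2725, and 0.50 × 0.50 + 0.45 × 0.05 = 0.2725. Common drift cancels.

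**(1) No PDT effect, equal drift on both forearms, 5% changing the other way**

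| Drift | Treated-only, n=15 | n=16 | Between-side, n=15 | n=16 |
|---|---|---|---|---|
| 10% | 0.14% | 0.19% | 0.45% | 0.56% |
| 20% | 3.6% | 4.6% | 1.3% | 1.4% |
| 30% | 16.7% | 19.8% | 1.8% | 1.9% |
| 40% | 37.8% | 42.4% | 2.0% | 2.1% |
| 50% | 59.6% | 64.3% | 2.0% | 2.1% |

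Downward drift produces these rates as false improvement, and upward drift as false worsening.

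**(2) PDT lowers p53** (treated: 30/40/50% turn negative, 5% positive; control: 5% each way) **and (3) PDT holds skin steady** (treated: 5% each way; control: 30/40/50% turn positive, 5% negative)

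| Scenario | Test | n=15 | n=16 |
|---|---|---|---|
| 2 | Treated-only | 16.7 / 37.8 / 59.6% | 19.8 / 42.4 / 64.3% |
| 2 | Between-side | 14.7 / 31.5 / 51.0% | 17.0 / 35.1 / 55.3% |
| 3 | Treated-only | 0.0065% | 0.0095% |
| 3 | Between-side | 14.7 / 31.5 / 51.0% | 17.0 / 35.1 / 55.3% |

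Between-side power is the same in (2) and (3) because the difference probabilities agree. At 50%, (2) gives 0.50 × 0.95 + 0.45 × 0.05 = 0.4975 and (3) gives 0.05 × 0.95 + 0.90 × 0.50 = 0.4975; the opposite probability is 0.07 in both.

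The treated-only rates in (1) and (2) are identical. The planned test cannot tell a real PDT effect from common drift of the same size.

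**The case against.** - **The wording may be loose.** Section 6.1 requires the treatment fields to be free of NMSC and recent AK, and footnote E of the schedule describes the screening skin examination as one of the treatment area. A split-side trial would need both to cover the control side too, so Section 17.2 could have meant both forearms. This is fair. But Section 17.2 separates the two sides for every other measure, so the literal reading is the better one. If Section 16 meant McNemar's test between forearms, Section 17.2 supplies no control-side p53 for it. The sections need reconciling on any reading.
- **The stakes are limited.** This is a pilot of 16-20 subjects, p53 is a secondary measure outside the Section 1.3 list, and nothing says it will support an efficacy claim. This stands and limits the weight of the point.
- **The drift is hypothetical.** The high rates need 30-50% of sites to shift one way without PDT. In immunosuppressed patients with sun-damaged skin, upward drift may be likelier, which works against a false benefit. That is reasonable, but staining batches or better sun protection could push p53 down, and upward drift on the control side is the situation in which the treated-only test misses a benefit.
- **The treated-only test has more power if PDT lowers p53**, 60-64% against 51-55% at the largest effect. True, but it shows the same rates with no PDT effect.
- **Karyometry is not wholly unspecified.** The fields and times are given; the summary measure, between-side contrast and test are missing. Taken alone that is missing detail, and the main point does not rest on it.

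**Conclusion.** The concern holds. Followed as written, the p53 test cannot attribute a change in either direction to PDT, because it leaves out the randomized control forearm although that tissue is collected at both times. This conclusion comes from the design and does not depend on the assumed rates.

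The size does depend on them. Under the assumptions above, common drift of 30-50% with no PDT effect makes the treated-only test significant in 17-64% of trials, against at most 2.1% for the between-side test. At 20% drift or less the treated-only rate is under 5%. If PDT only holds treated skin steady, the treated-only test detects it in under 0.01% of trials, against 15-55% between sides.

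This should be corrected, but it is confined to secondary measures. The primary lesion count is compared between sides and is unaffected.

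**What to change.** 1. **p53, minimum.** In Section 16, label the treated-side change as descriptive, with no efficacy claim.
2. **p53, if a test is wanted.** Stain the existing control-forearm biopsies as well, define the score, and test treated-minus-control change within patient: exact sign test if positive/negative, Wilcoxon signed-rank if graded. Report an estimate and confidence interval, because power is limited at 15-16 subjects. Since the treated side is randomized, McNemar's test between forearms at end of treatment is another valid choice and keeps the named test.
3. **Karyometry.** In Section 16, name one karyometric summary per biopsy and test the within-patient difference in change, treated minus control forearm, by Wilcoxon signed-rank.
4. **Consistency.** State the role of p53 in the same way in Sections 1.3, 10.2, 16, 17.2 and 26.

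Items 1, 3 and 4 cost wording only. Item 2 is optional and adds two stained sections per subject, 2 × 16 = 32 to 2 × 20 = 40 in all, with no new biopsies.

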9.4 End of Intervention

Subjects will have their last PDT treatment at visit 9 which will be considered off treatment when the visit is completed.

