26. SCHEMA OR STUDY SCHEDULE

Study Procedures	Screening/ Baseline ^A	On Study Treatment ^B								Early Termination	End of Study ^c
		Day 1	Day 30	Day 180	12 Month	18 Month	24 Month	30 Month	36 Month		
Visits	1	2	3	4	5	6	7	8	9	ET	EOS
Eligibility Verification	x										
Informed Consent	x										
Registration	x										
Medical History ^D	x										
Physical Exam ^E	x										
Concomitant medications	x	x	x	x	x	x	x	x	x		
Levulan-PDT		x	x	x	x	x	x	x	x		
Adverse events		x	x	x	x	x	x	x	x	x	
Punch Biopsy ^F		x							x		
VAS Scale ^G		x	x	x	x	x	x	x	x		
Sun Damage Scale ^H		x	x	x	x	x	x	x	x	x	x
Photographs ^I		x	x	x	x	x	x	x	x	x	x

^A Screening may be conducted within 28 days before first treatment.

^B Treatments may be conducted \pm 3 days for Day 30 treatment and \pm 30 days for Day 180, 1 year, 1.5 year, 2 year, 2.5 year, and 3 year visits respectively. Treatment visits are based on the Initial Day 1 treatment visit.

^C 3 months (\pm 30 days) after the last treatment.

^D Medical history including past medical, meds, allergies, social and HPI will be done.

^E Physical exam will consist of vital signs (blood pressure & pulse), and a full treatment area skin exam.

^F Punch biopsies will be used for karyometric analysis between baseline and end of treatment.

^G For more information about the VAS Scale, please refer to Appendix 1.

^H For more information about the Sun Damage Scale, please refer to Appendix 2.

^I For more information about digital photography, please refer to Appendix 3.

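### The final (Month 36) punch biopsy is placed at the visit of the last PDT and after it, so the p53 and karyometry changes can include an acute effect of that session

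*Combined protocol and SAP*

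**What the plan says.** Five places in the combined protocol and SAP bear on the timing of the biopsies.

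- **Section 10.1 (Collection).** Each forearm is sampled twice by punch biopsy. The timing of the baseline sample is "prior to the first session". For the final sample, which also covers both forearms, the section says that it "will be taken at the end of all the sessions at 3 years".
- **Section 17.2 (Efficacy Analysis).** Epidermal dysplasia is rated by "p53 staining of skin biopsies in the treatment areas at baseline and after the last treatment". Only the treatment areas are named.
- **Section 9.4 (End of Intervention).** "Subjects will have their last PDT treatment at visit 9".
- **Section 26 (schedule).** The punch biopsy is marked at Day 1 (visit 2) and Month 36 (visit 9) only. Levulan-PDT is also marked at both visits. No biopsy is marked at Early Termination or at End of Study, which falls 3 months (± 30 days) after the last treatment. Footnote F adds: "Punch biopsies will be used for karyometric analysis between baseline and end of treatment".
- **Sections 1.3 and 16.** Section 1.3 lists change in karyometry from baseline in treated and untreated fields. Section 16 tests the change in p53 staining from baseline to end of treatment with McNemar's test and expects 15-16 evaluable subjects.

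No section states a minimum interval between the last PDT and the final biopsy.

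**The concern.** The biomarkers are there to show whether three years of cyclic PDT changed the field damage in the skin. That needs baseline and final tissue in comparable states, differing only in the long-term effect of treatment. Baseline tissue has had no study PDT. Final treated-side tissue, on the plan's wording, has just been through a session.

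The protocol itself makes an acute response plausible. Section 4.1 describes the PDT reaction as able to cause toxicity and cell death rapidly. Section 4.4 says that p53 family members "may be important mediators of cell death signaling in photodynamic therapy of cancer". The marker chosen to rate dysplasia is thus also named as a possible marker of the response to the session.

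If an acute response is present in the final sample, it could mask a real long-term benefit or produce an apparent change that is not long-term.

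**Working it through.** **Step 1: order of events at visit 9.**

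| Source | What it fixes |
|---|---|
| 9.4 | Last PDT is at visit 9 |
| 26 | Final biopsy is at visit 9; none at End of Study |
| 10.1 | Final biopsy follows the end of all sessions |
| 17.2 | p53 tissue follows the last treatment |
| 10.1 | Baseline biopsy precedes the first session |

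The schedule gives the visit but not the order within it. The order comes from 10.1 and 17.2. Combined, they put the final biopsy at visit 9 and after that visit's PDT. Sampling before the session would not fit the wording of either section.

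**Step 2: can the planned comparisons remove an acute effect?** Let L be the long-term change on the treated side, A the acute change from the last session, and C the change over time on the untreated side.

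- p53, before versus after in treatment areas only: observed change = L + A. No control comparison is planned.
- Karyometry, treated versus untreated: (L + A) − C. The untreated forearm receives no PDT, so subtracting C leaves A in place.

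There is one post-baseline sample per forearm and no later one, so A cannot be estimated from the trial's data.

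**Step 3: interval from the latest PDT to the final biopsy.** Taking a month as 30.4375 days and ignoring any treatment delay under section 8.3:

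- As written: same visit, interval not stated.
- Visit 9 before PDT: 6 × 30.4375 ≈ 183 days after the Month 30 session. With ± 30 days at both visits, about 123 to 243 days.
- End of Study: about 90 days after the last PDT, 60 to 120 with the window.

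The sessions are Day 1, Day 30, Day 180 and Months 12, 18, 24, 30 and 36, eight in all. Tissue taken before the last one reflects seven.

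**Step 4: illustration for p53.** The documents give no rates, so every rate here is assumed, including the direction of the acute effect. No figure in the plan is available to reproduce.

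Assume n = 16 and 60% positive at baseline. The exact two-sided McNemar p-value is 2 × P(Bin(b + c, 0.5) ≤ min(b, c)), capped at 1, where b counts positive-to-negative and c negative-to-positive changes. Six changes all in one direction are needed for significance (2 × 0.5⁶ = 0.031; five give 0.0625). Power is summed over all (b, c).

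*(a) Acute effect raises staining.* Let k be the share of positives cleared long term, let 5% of negatives turn positive, and let q be the share of otherwise negative final samples turned positive by the session. Then P(b) = 0.6 × k × (1 − q) and P(c) = 0.4 × (0.05 + 0.95q). For k = 0.7:

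| q | P(b) | P(c) | Power |
|---|---|---|---|
| 0 | 0.420 | 0.020 | 61% |
| 0.1 | 0.378 | 0.058 | 34% |
| 0.2 | 0.336 | 0.096 | 17% |
| 0.3 | 0.294 | 0.134 | 7% |

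With k from 0.5 to 0.9, power runs from 27% to 85% at q = 0 and from 6% to 33% at q = 0.2.

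*(b) Acute effect lowers staining, with no long-term change.* Let q be the share of otherwise positive final samples that lose staining. Then P(b) = 0.6q and P(c) = 0, and a false finding of benefit needs b ≥ 6 of 16. Its probability is 0.8% at q = 0.2 (P(b) = 0.12), 5% at q = 0.3 (P(b) = 0.18) and 34% at q = 0.5 (P(b) = 0.30).

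In (a), a modest acute effect is enough to hide a benefit. In (b), only a large one often creates a false benefit.

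**The case against.** The strongest reply is that no single sentence says the biopsy is taken on the day of the last PDT and after illumination. The schedule does not order procedures within a visit. The phrase in 10.1, "will be taken at the end of all the sessions at 3 years", could mean the end of the treatment course, and 10.1 does state an order relative to a session when it wants one, at baseline. Section 17.2 describes what is rated and not how tissue is collected. Section 16 and footnote F say only end of treatment. This stands in part: the order is a reading of several sections together, which limits confidence to moderate. It is still the reading that the wording of 10.1 and 17.2 favours, and nothing in the plan prevents a site from following it.

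The second reply is that no acute effect on these readouts is shown. This stands. Sections 4.1 and 4.4 make one plausible but do not show that p53 staining or nuclear measures would change in tissue taken very soon after illumination. If the interval is very short, the effect could be small. The illustration shows sensitivity to assumed rates and is not evidence of bias.

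A reader might infer three stronger points that the documents do not support:

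- **That the biomarker results will be biased, or cannot be interpreted.** No size, direction or time course is given.
- **That treated and control specimens are unequally exposed for both markers.** That asymmetry matters for karyometry. p53 is rated in treatment areas only, so its problem is purely before versus after.
- **That the trial's main conclusions are at risk.** They do not rest on this tissue.

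**Conclusion.** The point holds as a risk of confounding of unknown size and direction, with moderate confidence. It rests on reading 9.4, 10.1, 17.2 and the schedule together, and on an acute response that the protocol's background makes plausible but does not quantify. If sites follow that reading, every treated-side final specimen is exposed to it and no control-side specimen is.

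The reach is narrow. Karyometry is listed after the primary endpoint in 1.3, and section 16 names no test for it. p53 is a secondary measure in section 16 and is not listed in 1.3. The primary AK/NMSC count, time to first lesion and the safety analysis do not use these biopsies. The point still deserves action because the ambiguity cannot be repaired in analysis once the tissue has been taken.

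**What to change.** **Preferred.** In 10.1, 17.2 and the schedule, state that the final biopsies on both forearms are taken at visit 9 before the Month 36 PDT. Change the 17.2 wording that places the sample after the last treatment, and the matching phrase in 10.1. This mirrors the baseline sample, which the plan already takes before the Day 1 session. The cost is that the tissue reflects seven sessions instead of eight, so the text should describe it that way.

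**Alternative.** Move both final biopsies to the existing End of Study visit and mark them there in the schedule. The tissue then reflects all eight sessions. Subjects who miss that visit contribute no final tissue. This loss should be small, because section 16 already restricts efficacy-evaluable subjects to those completing all study visits. Section 2.4 would also need reconciling: it gives participation of about 37 months, whereas End of Study falls at about 36 + 3 = 39 months after Day 1.

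The documents do not say how long an acute effect lasts, so neither option can be called free of it. The first leaves the longer interval. Both need wording only, with the same number of biopsies and visits. The change should be made before the first subject reaches Month 36.
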